### **Specific Aim 3: Dyspnea on Exertion in Obese Children**

Introduction: DOE During Constant Load Submaximal Exercise. The *working hypothesis* is that childhood obesity will increase DOE and alter respiratory function during constant load submaximal cycling, but to a greater extent in obese children with respiratory symptoms misdiagnosed as asthma. The *rationale* behind the proposed research centers on the fact that exercising will force EELV to even lower levels in obese children creating the potential for significant breathing limitations. If low enough, obese children could experience tidal expiratory flow limitation, constrained expiratory tidal volume expansion, and decreased ventilatory capacity. It is unclear whether these respiratory effects or changes in body composition will be linked with DOE in obese children (i.e., increased RPB as it is in obese adults). Furthermore, we propose that obese children with respiratory symptoms misdiagnosed as asthma will have greater changes in EELV or differences in peripheral airways function making them more susceptible to the limitations of low lung volume breathing and/or increased ratings of dyspnea on exertion.

Methodology, experimental protocol, and measurements. The strategy will be to determine respiratory function, breathing mechanics, and DOE during 6 minutes of constant load submaximal exercise cycling at 30W (8-9 yr olds) or 40W (10-12 yr olds) and during 6 minutes of constant load cycling at 50% of peak  $\dot{V}O_2$ . We will measure HR, BP, SpO2%, PETCO2, gas

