Interpretation of results. We will interpret these results to suggest that obese children have significant obesity-related alterations in DOE and respiratory function during submaximal exercise, which predispose them to potentially clinical breathing limitations, especially in obese children misdiagnosed with asthma, all through a common mechanism of low lung volume breathing. This is important knowledge for the healthcare provider who sees obese children with symptoms on exertion. On the other hand, if obese children have RPB values similar to that in nonobese children during exercise, without association with other obesity-related changes, this would imply that increased chest wall fat and a lower EELV do not impair breathing during exercise as in obese adults, which would be important to document.

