Expected results. We expect that a program of weight loss (or an equivalent reduction in BMI percentile) and regular exercise will increase FRC at rest and EELV during exercise while weight gain will decrease these. The change in FRC and EELV may be correlated with changes in body composition (if any). These improvements in respiratory function and breathing mechanics may also be associated with decreased DOE as well, while weight gain would have the reverse effects. Exercise tolerance will be increased in ml/min/kg but we expect no change in cardiorespiratory fitness (i.e., Peak  $\dot{V}O_2$  as percent predicted based on ideal body weight), which may actually be slightly decreased, including those misdiagnosed with asthma. With weight gain, exercise tolerance will be decreased but cardiorespiratory fitness would be unchanged as well. We also *expect* to have a better understanding of the importance of weight loss and regular exercise and weight gain on respiratory function and breathing mechanics in obese children, and the differences (if any) between obese boys and girls.

Interpretation of results. We will interpret these results to suggest that weight loss (or an equivalent reduction in BMI percentile) and regular exercise will have a significant improvement on respiratory function, exercise tolerance, and DOE, while weight gain will worsen respiratory function, exercise tolerance, and DOE in obese children all through a common mechanism of increasing or decreasing EELV. Weight loss may also reduce potential clinical breathing limitations at rest and during exercise (e.g., expiratory flow limitation) but weight gain would increase limitations. This would be important knowledge for healthcare providers who may not appreciate the obesity-related respiratory effects in obese children, and who may assume that

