symptoms such as breathlessness are just due to cardiovascular deconditioning and/or asthma. In contrast, if obese children have a simple increase in EELV with weight loss without association with other changes in respiratory function, exercise tolerance, and DOE, this would be clinically important to document as well. The same would be true if there were no negative effects of weight gain. These findings, while very unlikely, would suggest that chest wall fat and changes in respiratory function are not the lone sources of obesity-related breathing limitations and bring to question what effects weight loss and regular exercise, and weight gain might have on respiratory function, exercise tolerance, and DOE.

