**Aim 4.** Primary variables for Aim 4 are change in FRC at rest, peak  $\dot{V}O_2$ , RPB, and EELV during constant load exercise from before to after 1 year of follow-up. We are gaining experience with studies in children; current preliminary data from n=7 obese children yield similar mean differences and standard deviations as in adults. Therefore, based upon the change in EELV during constant load exercise in obese men before ( $35 \pm 5$ ) and after ( $39 \pm 3$ ) a loss of 13% of body fat, and the change in RPB during constant load exercise in obese women before ( $4.7 \pm 1.1$ ) and after ( $3.2 \pm 1.6$ ) weight loss, our sample will have sufficient power (.80,  $\alpha=0.05$ ) to detect meaningful paired differences (e.g., 1.5 in RPB) with weight loss and regular exercise. We will retest all children after ~1 yr. We expect less than 10% attrition and repeated data on nearly all children will be available for this Aim. Combining the two obese groups (with and with asthma misdiagnosis), the children will be divided into obese who lost weight, obese who gained weight, and control normal weight children and respiratory changes will be compared between groups with ANOVA as described for Aims 1-3. While these categorized weight changes have clinical appeal, weight change analyzed as a continuous variable may be more powerful and informative. Hence, change at 1 year minus baseline will also be evaluated with Spearman or Pearson correlations to quantify the association between 1-year weight change and the change for respiratory function, exercise tolerance, and DOE variables and, with the 36 obese participants analyzed (by gender), a correlation of 0.45 can be detected with 80% power.

To evaluate gender effects, baseline and follow-up measurements for FRC, peak  $\dot{V}O_2$ , RPB, and EELV will be analyzed in mixed-effects repeated measures models with the study participant included as a random effect. Interactions between gender, study group (obese, obese misdiagnosed with asthma, nonobese), and time can be assessed as fixed effects; weight change effect will be modeled as a covariate. PAQ-C score changes will also be assessed with repeated measures models.

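### The conclusion that breathlessness changes through end-expiratory lung volume depends on an EELV–breathlessness association that no planned analysis estimates

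*Combined protocol and SAP*

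**What the plan says.** **Mechanism wording.** Under Specific Aim 4, Interpretation of results, improvement after weight loss and worsening after weight gain in function, exercise tolerance and dyspnea on exertion (DOE) are to be read as arising "all through a common mechanism of increasing or decreasing EELV". Under Specific Aim 3, Interpretation of results, differences in DOE and respiratory function during submaximal exercise are to be read as leading to breathing limitations "all through a common mechanism of low lung volume breathing".

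**Other conclusions foreseen.** The Aim 4 Expected results treat the link as a possibility: "These improvements in respiratory function and breathing mechanics may also be associated with decreased DOE as well". The Aim 4 interpretation then considers "a simple increase in EELV with weight loss without association with other changes in respiratory function, exercise tolerance, and DOE", and says such findings, which it regards as very unlikely, "would suggest that chest wall fat and changes in respiratory function are not the lone sources of obesity-related breathing limitations". Aim 3 gives another reading for the case where RPB does not differ between obese and nonobese children and is unrelated to the other effects of obesity: "this would imply that increased chest wall fat and a lower EELV do not impair breathing during exercise as in obese adults". The Aim 3 introduction calls the link with DOE unclear.

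**Planned analyses.** Statistical Considerations gives ANOVA and contrasts between groups for each variable (Aims 1–3). For Aim 4 it gives ANOVA between weight-loss, weight-gain and control groups, and Pearson or Spearman correlations "to quantify the association between 1-year weight change and the change for respiratory function, exercise tolerance, and DOE variables". It adds mixed models for FRC, peak VO2, RPB and EELV with weight change as a covariate. EELV is never named as a predictor of RPB.

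**The concern.** The narrative sets out two sets of conclusions and makes the choice between them turn largely on whether EELV and breathlessness are associated. The statistical section supplies neither an estimate of that association nor a criterion for judging it. If weight lowers EELV and, by another route, raises RPB, every planned comparison can come out as hoped, and the natural reading is then the mechanism statement.

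This is the study's main explanatory claim, and the plan's own preliminary data leave it open. Under Aim 3 of Statistical Considerations, RPB at constant load was almost the same in nonobese and obese girls (3.4±0.6 against 3.3±1.5), while the same paragraph stresses how low exercise EELV is in obese children. Those samples are small, but they are a reason to test the link directly.

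**Working it through.** **Inputs from the documents (Statistical Considerations).** 36 obese children per gender, so 72 in all; detectable correlation 0.45 at 80% power; alpha 0.05 (sidedness not stated, two-sided assumed); attrition below 10%, so 0.9 × 36 = 32.4 per gender and 0.9 × 72 = 64.8 pooled.

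**Assumed, not in the documents.** Correlations of 0.45 and 0.60 in size between weight change and each of EELV change and RPB change. The 0.45 is the plan's detectable value, not an expected one.

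**Step 1: reproduce the plan's figure.** Power = Φ(atanh(r)·√(n−3) − 1.96). With r = 0.45 and n = 36: atanh(0.45) = 0.485, √33 = 5.745, product 2.784, and Φ(0.824) = 0.795. Simulation of the t-test of r gives 0.806. The stated 80% is correct before attrition; at n = 32–33 it is about 74–76%.

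**Step 2: can the planned correlations tell the two explanations apart?** Write W, E and B for the changes in weight, EELV and RPB, with correlations given in size. Take r(W,E) = 0.60 and r(W,B) = 0.45 as observed.

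- *EELV is the only route.* Then r(W,B) = r(W,E)·r(E,B), so r(E,B) = 0.45/0.60 = 0.75. Given W, the partial correlation of E and B is (0.75 − 0.27)/√((1 − 0.36)(1 − 0.2025)) = 0.48/0.714 = 0.67.
- *Weight acts on each separately.* Then r(E,B) = 0.60 × 0.45 = 0.27, and the partial correlation given W is 0.

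The two planned correlations, 0.60 and 0.45, are identical in both cases. Only the EELV–RPB association given weight differs: 0.67 against 0. The same holds for the group ANOVAs, which use one outcome at a time.

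**Step 3: how often would the planned results look supportive with no link beyond weight?** Simulation, 50,000 runs, weight acting separately on E and B with equal correlations:

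| n | correlation with weight | both weight correlations p<0.05 | raw E–B p<0.05 | partial E–B given weight p<0.05 |
|---|---|---|---|---|
| 36 | 0.45 | 66% | 22% | 5% |
| 36 | 0.60 | 96% | 59% | 5% |
| 72 | 0.45 | 96% | 40% | 5% |
| 72 | 0.60 | >99% | 88% | 5% |

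The 5% is simply alpha, since no partial link was built in. The informative columns are the third and fourth. The planned results look supportive most of the time, and a raw EELV–RPB correlation would also mislead, so adjustment for weight is needed.

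**Step 4: can this sample carry the missing analysis?** Detectable r at 80% power = tanh((1.960 + 0.842)/√(n−3)).

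- n = 36: tanh(2.802/5.745) = 0.45; n = 33–32: 0.47–0.48.
- n = 72: tanh(2.802/8.307) = 0.325, about 0.33; n = 65–64: about 0.34.

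With two covariates, n − 3 becomes n − 5. At n = 72 this gives tanh(2.802/√67) = 0.33, so gender and weight change cost little in this approximation.

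**The case against.** The strongest reply is that the plan already makes its conclusion conditional. A reader who stops at the mechanism wording might infer that it would be asserted even if EELV and breathlessness were unrelated. The documents do not support that: Aims 3 and 4 each state another conclusion. This part of the reply stands. What it leaves open is how the alternative would be recognised. The Aim 4 alternative turns on an absence of association, which nothing planned measures. The Aim 3 alternative starts from similar RPB between groups, so it does not cover the case where RPB and EELV both differ for separate reasons.

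Three further readings are tempting and should not be pressed.

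- **RPB is compared only at fixed watts, so heavier children do more work.** The plan also has a bout at 50% of peak VO2, chosen to examine RPB and EELV at equal relative intensity, and it chose cycling because body weight affects it less. That eases the work-rate concern; it does not test an EELV–RPB link.
- **Airway function is a rival route.** Aim 3 does write "greater changes in EELV or differences in peripheral airways function making them more susceptible", but the sentence goes on to susceptibility to low lung volume breathing (or greater breathlessness), so airway function appears mainly as a modifier.
- **Aims 1a and 1b make the same claim.** Their common-mechanism wording concerns resting function that may predispose to limitation, not a link between EELV and RPB.

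It is also fair that the simulation is illustrative, that non-significance at this sample size is not absence, and that adjustment for ventilation may remove part of the hypothesised pathway. These points shape the fix below.

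**Conclusion.** The point holds in this form: Aims 3 and 4 state what would be concluded with and without an association, but the statistical section contains no analysis relating EELV to RPB, and its weight-change correlations and group comparisons would look the same under an EELV route or parallel effects of weight. No stated number is wrong, and the r = 0.45 figure reproduces.

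The size of the problem cannot be fixed from the documents. If weight change correlates 0.45 to 0.60 with both outcomes and acts on them separately, both planned correlations are significant in about 66% to 96% of studies at n = 36. This rests on those assumed correlations, on a two-sided test, and on no link beyond weight. The structural conclusion, from Step 2, does not depend on the particular values.

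Even the right analysis would show association in non-randomised groups, so it could support the mechanism but not establish it. This is a cheap improvement, not a flaw in the study's primary comparisons.

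**What to change.** In Statistical Considerations, add the following.

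1. **Aim 4.** Regress 1-year change in RPB on change in EELV (%TLC) during constant-load exercise in the obese children, pooled over gender (about 72 before attrition), with gender and weight change as covariates.
2. **Aim 3.** In the obese children at baseline, regress RPB on EELV (%TLC) at the same bout, adjusted for gender and a baseline measure of body size or fatness. Do this for both the fixed-watt and the 50% peak VO2 bouts.
3. **Sensitivity.** Repeat both with adjustment for minute ventilation, labelled as sensitivity analyses because ventilation may lie on the pathway.
4. **Reporting rule.** Give estimates with confidence intervals. Use the Aim 4 mechanism wording only if the adjusted association is supported, and then as findings consistent with an EELV mechanism. If the interval is wide and includes zero, say that the link was not shown, not that it is absent.
5. **Sensitivity of the design.** State that the detectable correlation at 80% power is about 0.33 pooled and about 0.45 per gender, before attrition.

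EELV, RPB, ventilation and body composition are already measured, so no new data are needed. The cost is a little more analysis and a more conditional conclusion.

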### **Subject Selection**

Prepubescence. We have elected to study the effects of obesity in otherwise healthy prepubescent children for three reasons. One, this level of obesity is very prevalent in prepubescent children. Two, they may benefit the most from early intervention to prevent the development of further obesity, increased cardiovascular risk factors, and/or comorbidities like type-2 diabetes, which usually manifest after puberty. Three, boys and girls should have very similar predicted respiratory function values and pubertal effects on exercise responses should be minimal.

Matching of groups. Nonobese children will have age and sex specific BMI between 16th and 84th percentile in order to exclude children who are overweight and/or possibly underweight. Both the groups will be otherwise healthy since most obesity-related metabolic issues occur after puberty.

Recruitment of subjects. We will recruit participants by BMI percentile, age, and gender only. We will recruit participants from large pediatric practices, Children’s clinics (My Children’s Clinics), emails throughout Texas Health Hospital System, paid sites such as Center Watch and Sunshine Day, community programs (e.g., 7 Day Fitness Academy, Parkland Hospital Health Camps, Get UP and Go programs), advertisements in local newspapers, and ads in other media sources). Also, approximately 1250 patients enter the **COACH** program per year with an average age of 11.6±2.9 yr. Males make up 42% of the population and race/ethnic background is approximately 55/25/4/16 (W/AA/H/O). We are very confident in our ability to recruit and retain participants. Our preliminary retention numbers are quite good (14 of 16). Also, based upon our preliminary data, 50% of the obese children we tested last summer lost weight and 50% gained weight, and we had no contact with these children since last summer. We will recruit heavily before and during summer. We will recruit, and search COACH and medical practice records for children diagnosed with asthma who have not had pulmonary function tests to confirm the presence of asthma.

Subjects. A total of 96 prepubescent children, 48 boys (36 obese) and 48 girls (36 obese), who are otherwise healthy, will complete all four aims. 24 of these obese children (12 girls & 12 boys) may have respiratory symptoms, which were misdiagnosed as asthma (i.e., not confirmed by lung function tests). We will confirm the absence of asthma by spirometry before and after bronchodilator, and by bronchial challenge test with methacholine. We will include children between **8-12** years old as long as they have a **Tanner stage ≤ 3** and can successfully perform pulmonary function tests, exercise tests, and ratings of breathlessness. We anticipate that children less than 8 yr old could have difficulty performing accurate pulmonary function and exercise tests and will be excluded from participation. Including children within 8-12 years old should increase the likelihood of meeting our recruitment goals. In future studies we anticipate studying older children and adolescents (also see Subject criteria Human Subjects Section).

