### **Statistical Considerations**

Co-investigator [name] (UT Southwestern Division of Biostatistics) is the statistical co-investigator on this project and has assisted in the development of the statistical plan; she will also

Total n=96	Obese	Obese misdiagnosed with asthma	Non- obese
Boys	n=24	n=12	n=12
Girls	n=24	n=12	n=12

direct the data analysis on an on-going basis.

Statistical Plan. Our plan is to complete testing in nonobese and two obese groups, boys and girls separately but concurrently. Thus, sample size calculations are based upon within-gender comparisons per allocation in table at right. In Aims 1-3, comparisons will be made between nonobese, obese, and obese children misdiagnosed with asthma within the same gender with analysis of variance models (ANOVA). Pairwise group comparisons will be made using least squares means contrasts derived from the linear models. Data transformations or nonparametric tests will be utilized as needed to meet analysis assumptions. At baseline, ISSAC and ECRHS asthma screening questionnaire scores will be compared among groups with the Kruskal-Wallis test. Comparisons for Aim 4 will be made similarly, but with the addition of repeated measurements to assess the two obese groups and the nonobese children of the same gender at baseline and at 1 year of follow-up. Additional assessments of gender effects will be performed as part of a secondary analysis, but we are not powering the study to detect interaction by gender. Alpha is set at 0.05 for ANOVA and planned contrast power (PASS 11, NCSS, LLC, Kaysville, UT), described below . Data will be analyzed using SAS version 9.4 (SAS Institute, Inc., Cary, NC).

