Aim 1. Our primary variable is FRC measured while seated upright (Aim 1a) and when lying supine (Aim 1b). Based upon our preliminary data for seated FRC (%TLC) in nonobese boys (mean± SD, 42.4±2.5) and obese boys (36.5±6.2), it is calculated that a mean difference in FRC (%TLC) of 5.1 can be detected with statistical power of 81%, alpha=0.05, pooled SD of 5.0, comparing 24 obese to 12 nonobese children or to 12 obese children misdiagnosed with asthma. Our data also show that the differences may be larger for girls than boys, so power for a test between obese girls and obese girls misdiagnosed with asthma will be at least 80%. Similarly, for children lying supine, nonobese boys have an FRC (%TLC) of 34.4±8.8 vs. 23.1±3.4 obese, a more conservative difference of 6.0 %TLC is detectable with 80% power. In our formal protocol, we anticipate being able to make precise and reproducible measurements, and have confidence that we can meet our goals with the sample size proposed. Preliminary data demonstrate that these measures and effect sizes are feasible.

Aim 2. Our primary variable is peak  $\dot{V}O_2$ . From our preliminary peak  $\dot{V}O_2$  (ml/min/kg) for nonobese (41.9±4.9) and obese boys (26.3±3.9), it is calculated that our study will yield power of 80% to detect a clinically relevant mean difference of 4.7 ml/min/kg for obese versus nonobese children or obese children misdiagnosed with asthma, anticipating smaller differences than the 16 ml/min/kg mean difference observed from our data in obese versus nonobese. Effect size estimates for girls are anticipated to be similar.

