#### **Anticipated problems and potential solutions**

The anticipated changes in respiratory function (particularly FRC) should be apparent at this level of obesity. A 10.5 yr old boy at 4' 8 1/2" or 143.3 cm at the 95th percentile will have a body mass of 103-105 lb. The upper limit for that same child at 150% of the 95th BMI percentile is 155 lbs. Thus, the range for this example child is ~50 lbs (22.7 kg). This increase in weight is significant and should produce the type of effects we expect as confirmed in our preliminary data. However, if this does not hold true, we do not believe increasing the range of obesity to include those with BMI scores > 150% of the 95th percentile would yield a subject population that is representative of the majority of obese children. We intend to perform testing for Aims 1a and 1b in two sessions ( $\approx 2.5$  hr each). This approach has been very attractive to the children and parents without complaint and the children have performed upright and supine respiratory function tests without difficulty. Also, if the weight placed on the abdomen is not tolerable, we will investigate other methods like a weighted vest or broader distribution of the weight over the chest wall. We have not found our standard graded cycle ergometry protocol to be a problem when testing peak performance in obese or nonobese children, especially when confirmed at supra-maximal work rates. However, if we find the protocol difficult for them, we can try different stage increments, or try a non-continuous exercise test to determine peak exercise capacity. Also, we believe that the level of obesity planned for this study will not preclude the obese children from completing exercise testing at 30 or 40W as in the nonobese children or with our ability to examine respiratory function, breathing mechanics, and DOE during exercise at 30 or 40W. Nevertheless, we will complete a second exercise session at 50% of peak  $\dot{V}O_2$  just to be sure. So far all procedures and testing has been very well-tolerated and without complaint. Weight loss success is always a concern that involves many personal and family-related issues.

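### The obese versus misdiagnosed contrast in Aims 1-3 has no control for degree of obesity beyond a wide shared eligibility band, so a difference in fatness could create or hide a difference between the groups

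*Combined protocol and SAP*

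**What the plan says.** **Eligibility and recruitment.** Overall Strategy gives both obese groups the same BMI band, above the 95th percentile and below 150% of it. Anticipated problems puts the width of that band in pounds: "Thus, the range for this example child is ~50 lbs (22.7 kg"). It adds that a weight increase of this size should produce the expected effects. Under Subject Selection, the paragraph on matching sets the BMI range of the nonobese children and says the groups are otherwise healthy. It matches nothing between the two obese groups. The recruitment paragraph says "We will recruit participants by BMI percentile, age, and gender only", while Overall Strategy notes that percentile curves are inaccurate at the extreme tails. For the misdiagnosed group the investigators will also "search COACH and medical practice records for children diagnosed with asthma who have not had pulmonary function tests".

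**Analysis.** For Aims 1-3, Statistical Considerations states that "comparisons will be made between nonobese, obese, and obese children misdiagnosed with asthma within the same gender with analysis of variance models (ANOVA"). Pairwise contrasts are least squares means from those models, and no covariate is named. The only covariate in the plan is 1-year weight change, in the Aim 4 mixed models. DEXA and anthropometry are collected to describe group differences (Aim 1a), and correlations with body composition are anticipated, but neither enters the group contrast.

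**Role of the contrast.** Greater changes in misdiagnosed children are hypothesised in Aims 1 and 3, and reduced fitness in Aim 2. The Aim 1 power statement covers the contrast: "a mean difference in FRC (%TLC) of 5.1 can be detected with statistical power of 81" per cent, with "pooled SD of 5.0, comparing 24 obese to 12 nonobese children or to 12 obese children misdiagnosed with asthma".

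**The concern.** The plan's own mechanism is that chest-wall fat lowers FRC and EELV. It also says that the spread of weight inside the eligibility band is large enough to matter. A difference in mean fatness between the two obese groups would therefore act directly on these outcomes. Peak VO2 in ml/min/kg is exposed as well, because body weight is its denominator. Peak VO2 as percent predicted on ideal body weight, the variable behind the Aim 2 fitness hypothesis, is less exposed.

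If the misdiagnosed children were fatter, a lower FRC could be read as greater susceptibility linked to their symptoms. If they were leaner, a real susceptibility could be hidden. The planned contrast cannot tell these cases apart. Yet Aim 1a speaks of children who are more susceptible to low lung volume breathing, and the Aim 3 interpretation singles out the misdiagnosed group.

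**Working it through.** **Step 1: the plan's own figure.** Inputs from Statistical Considerations, Aim 1: difference 5.1 %TLC, SD 5.0, 24 v 12 within gender. "Alpha is set at 0.05 for ANOVA and planned contrast power" gives the level. Sidedness is not stated, so two-sided is assumed.

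- SE = 5.0 × √(1/24 + 1/12) = 5.0 × 0.354 = 1.77 %TLC
- Noncentrality = 5.1/1.77 = 2.88
- Power by noncentral t = 80.0% with 34 df (two groups), or 80.6% with 45 df (three-group error term); the normal approximation gives 82.3%

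The stated 81% is reproduced. It is the power of an unadjusted contrast.

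**Step 2: bias of the unadjusted contrast.** Let r be the within-group correlation of seated FRC with fatness, and d the systematic difference in mean fatness between the obese groups, in SDs of fatness. The documents give neither, so both are assumed over a range. With no true group effect:

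- bias = r × d × 5.0
- false-positive rate = two-sided rejection probability of the noncentral t, 34 df, noncentrality = bias/1.77

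**Step 3: power after adjustment, same children.** For the obese-only contrast with one fatness covariate:

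- residual SD = 5.0 × √(1 − r²)
- variance inflation = 1 + d²/[34 × (1/24 + 1/12)] = 1 + d²/4.25, which is 1.06 at d = 0.5 and 1.24 at d = 1.0
- 33 df, true difference 5.1 %TLC

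| d (SD) | r | Spurious difference (%TLC) | Share of 5.1 | False-positive rate, unadjusted | Power, adjusted |
|---|---|---|---|---|---|
| 0.5 | 0.3 | 0.75 | 15% | 7.0% | 81% |
| 0.5 | 0.45 | 1.1 | 22% | 9.5% | 86% |
| 0.5 | 0.6 | 1.5 | 29% | 13.1% | 93% |
| 1.0 | 0.3 | 1.5 | 29% | 13.1% | 75% |
| 1.0 | 0.45 | 2.25 | 44% | 23.6% | 81% |
| 1.0 | 0.6 | 3.0 | 59% | 37.8% | 88% |

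If the covariate is unrelated to FRC (r = 0), there is no bias to remove, and adjusted power is 78% at d = 0.5 and 71% at d = 1.0.

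**Step 4: are these values of r plausible?** The preliminary seated data are "nonobese boys (mean± SD, 42.4±2.5) and obese boys (36.5±6.2"), a gap of 5.9 %TLC. Assume that the gap spans 35 to 50 points of percent of the 95th percentile.

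- Slope = 5.9/50 to 5.9/35 = 0.12 to 0.17 %TLC per point
- If obese children are spread evenly over 100-150%, the SD is 50/√12 = 14.4 points
- Implied r = 0.12 × 14.4/5.0 to 0.17 × 14.4/5.0 = about 0.35 to 0.49, inside the assumed range
- A 10-point imbalance (10/14.4 = 0.7 SD) gives 1.2 to 1.7 %TLC and a false-positive rate of about 10% to 15%

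**The case against.** **Partial control exists.** The shared band is control by restriction, BMI percentile is named as a recruitment variable, and the DEXA and anthropometric comparison would make an imbalance visible. This is true. But the band is wide by the protocol's own account, and seeing an imbalance does not remove it from the contrast. Least squares means could carry a covariate, but none is named. The protocol refers to a Human Subjects section that is not among the documents, so a balancing rule there cannot be excluded. The analysis gap would remain.

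**A reader might infer that the misdiagnosed children are fatter because they come from an obesity clinic.** The documents do not support this. The record search is added to general recruitment, and paediatric practices and COACH are sources for obese children generally. No difference in fatness is documented in either direction.

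**Chance imbalance.** With 24 v 12 the SE of the fatness difference is 0.35 SD, so a sizeable imbalance can arise by chance. That is already within the nominal 5%. Only a systematic difference inflates the rate.

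**Larger effects might be inferred for other outcomes.**

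- *Supine FRC.* Spreading the 11.3 %TLC supine gap over as few as 8 BMI units gives a slope of 1.4 per unit. The example child's band runs from BMI about 23 to 34 (SD about 3.2 if evenly spread). Fatness alone would then give an SD of about 4.6 %TLC, above the 3.4 reported for obese boys.
- *Peak VO2.* A 22% weight excess at unchanged absolute VO2 would turn 26.3 into 21.6 ml/min/kg, the whole 4.7 target. But 22% has no source and amounts to roughly half the band as a difference in means.

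Neither figure should be used.

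**Choice of estimand.** The expected results ask whether misdiagnosed children show greater changes, and the unadjusted contrast answers that. So it would be too strong to say that the stated question goes unanswered, or to forbid any claim without adjusted support. Fatness may also be part of why these children have symptoms, and chest-wall fat may lie on the causal pathway. This stands, and it is why both contrasts should be reported.

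**Conclusion.** The point holds as an analysis gap. In Aims 1-3 a non-randomised contrast that the plan powers and intends to interpret has no balancing and no adjustment for degree of obesity within a band of about 50 lb. Any systematic difference in fatness would bias FRC, EELV and peak VO2 in ml/min/kg, in a direction that cannot be known in advance.

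For seated FRC the size is 0.75-3.0 %TLC, with a false-positive rate of 7-38% in place of 5%. This rests on an assumed systematic imbalance of 0.5-1.0 SD and an assumed within-group correlation of 0.3-0.6. With no systematic imbalance, the planned contrast keeps its 5% level. The power calculation is not in error. The obese versus nonobese comparison, which leads each aim, is not affected by this point.

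**What to change.** In the Statistical Plan, for Aims 1-3:

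1. Add an obese versus misdiagnosed contrast, fitted among obese children only within gender, with baseline percent of the 95th BMI percentile as a covariate.
2. Report it beside the unadjusted contrast, together with the two groups' distributions of that covariate.
3. State what each contrast supports. The unadjusted one shows only whether misdiagnosed children are more affected. A claim of greater susceptibility at a given degree of obesity rests on the adjusted one.
4. Label any adjustment for DEXA chest-wall fat as exploratory, because it may be a mediator.

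**Cost.** No extra children or measurements are needed, since percent of the 95th percentile follows from the BMI already recorded. The adjusted contrast spends one degree of freedom and loses some precision to collinearity if the groups differ in fatness. Against the stated 81%, its power for 5.1 %TLC is about 81-93% at 0.5 SD imbalance and 75-88% at 1.0 SD. The lowest case examined is 71%, at 1.0 SD imbalance with a covariate unrelated to FRC.
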